**2. RESEARCH PLAN**

Purpose of Study:
This study will investigate if mindfulness training via a smartphone mobile app is effective in improving OA-related knee pain.
Hypotheses, Research Questions, or Objectives:

 
• Objective 1: Test whether use of a mindfulness mobile app improve knee pain in adults with knee OA among active duty and other DoD beneficiaries.
 
• Objective 2: Evaluate if self- reported, health-related quality of life and mindfulness scores predict response to mindfulness treatment in OA.
 
• Null Hypothesis 1: A mindfulness mobile app has no effect on knee pain in adults with knee OA.
 
• Alternative Hypothesis 1: A mindfulness mobile app improves knee pain in adults with knee OA.
 
• Null Hypothesis 2: Self- reported, health-related quality of life and mindfulness scores have no effect on response to mindfulness treatment in OA.
 
• Alternative Hypothesis 2: Self- reported, health-related quality of life and mindfulness scores predict response to mindfulness treatment in OA.
 

Significance:
Osteoarthritis (OA) is a major cause of disability in the United States and is expected to affect 26% of Americans by 2040  . Studies of the socioeconomic burden of OA demonstrate a 2-4 fold increase in healthcare expenditures for people with OA as compared to non-affected controls  . In addition, associated healthcare costs continue to rise: recent estimates of insurer and out of pocket healthcare costs of osteoarthritis exceed \$185 billion USD per year with another \$10 billion lost from absenteeism at work  .
Knee OA is one of the most commonly encountered diagnoses in the study team's sports medicine clinics. Despite the commonality of this condition, effective therapies are lacking as recent studies have called standard of care interventions into question, including NSAIDs, injectable, and surgery  . As a chronic, progressive disease, the management of OA centers on maximizing function while controlling pain. Conservative treatment options center on self-treatment modalities of therapeutic exercise programs (initiated through Physical Therapy), regular exercise, and weight control. Use of a mindfulness application may be another potential avenue of treatment. As the incidence of osteoarthritis rises, so does the projected physician shortfall. By 2030, this projected shortfall will reach 7,300-43,100 doctors  , highlighting the need for increased use of patient self-treatment modalities. There is a gap in the literature investigating the potential use of a mobile health application ("app")

as a biopsychosocial intervention to achieve improvement in knee pain, an approach that could be packaged readily for use in a clinical setting.

#### **Military Relevance:**

Osteoarthritis is a leading cause of pain and disability among adults worldwide; it is a very common and expensive ailment afflicting Active Duty and Retired Service Members as well as their dependents. Military members are more likely to experience osteoarthritis than their civilian counterparts, and the overall incidence of OA is rising in the military population, particularly among individuals nearing retirement. This study explores an inexpensive, noninvasive, self-directed treatment adjunct that may help better manage osteoarthritis-associated pain. Such a treatment may help to decrease costs associated with osteoarthritis disease management.

#### **Background and Review of Literature:**

Osteoarthritis (OA) is a progressive, degenerative joint disease and a leading cause of morbidity and disability worldwide. OA is estimated to affect 54.4 million adults, though recent studies suggest this commonly accepted number is greatly underestimated. Knee OA is the most common form of OA, and studies estimate that approximately 7% of Americans older than 25 (or 14 million people) have symptomatic knee OA. The lifetime risk of developing symptomatic knee OA is 45%.

There is a well-established bidirectional relationship between OA and mental health that suggests a role for biopsychosocial intervention in management of OA. The practice of mindfulness, classically defined by Kabat-Zinn as “the awareness that emerges through paying attention on purpose, in the present moment, and non-judgmentally to the unfolding of experience moment by moment”, may be an effective treatment for chronic pain. Studies of in-person mindfulness training have been shown to improve pain outcomes in those with both nonspecific and specific chronic pain, including pelvic pain and low back pain. In addition, mindfulness interventions have proven effective adjunct treatments for mood disorders, fibromyalgia, rheumatoid arthritis, and stress reduction in otherwise healthy patients. A recent systematic review of 13 randomized control trials found that mindfulness training improved patients’ perception of chronic pain and overall quality of life, suggesting it may be an effective adjunct treatment in the multidisciplinary approach to treatment of chronic pain. Regarding our specific population, a study of individuals with knee OA demonstrated that those with greater baseline mindfulness exhibited an improved self-perception in their physical quality of life and appeared to decrease the effect of pain on stress. In this same study group, those with higher total mindfulness scores were found to have a 38% greater response to a 12-week physical intervention (Tai Chi or physical therapy) than those with low mindfulness scores. One study found that 58% of individuals affected by OA had concomitant mental health disorder; the benefit of mindfulness training may demonstrate an increased effect in those with concomitant mood disorders.

To date, mindfulness studies involving chronic pain conditions have involved manpower- intensive interventions (in-person mindfulness training, group therapy, multiple physician appointments, etc.), which are difficult to implement in busy clinical settings. Web- and mobile health applications (mHealth) may provide an effective alternative to these interventions. A 2016 systematic review of 10 web-based mindfulness training programs found that such facilitator- free interventions were effective in reducing depression and anxiety. To our knowledge, only one protocol to date has been published investigating the use of a mindfulness mobile app as an intervention for improving outcomes in chronic pain.

Our primary aim in this study is to determine if regular use of a mindfulness application improves pain outcomes in adults with knee osteoarthritis. Our secondary aim is to determine if self-reported Healthcare-Related Quality of Life (HRQoL) scores predict response to mindfulness treatment in OA. We hypothesize that the use of an mHealth intervention for mindfulness training may be an effective adjunct treatment of chronic knee osteoarthritis pain; specifically, that regular use of a mindfulness application will result in a statistically significant reduction in pain outcomes and improvement in physical function as determined by the KOOS scoring system. We also hypothesize that those with lower baseline self-reported HRQoL scores are more likely to see a greater improvement in their pain and function with use of a mindfulness application than those with higher baseline scores.

### 3. RESEARCH DESIGN AND METHODS

#### **Research Design and Methods:**

Male and Female active duty members and DoD beneficiaries, ages 18 to 74 years old, meeting the inclusion/exclusion criteria will be offered an opportunity to participate. They will be recruited from the clinics located at Scott AFB, Nellis AFB, and Travis AFB. All of the below items are research-related unless marked as 'standard of care':

**Telephone Eligibility review:** We will obtain the potential subject's permission to be contacted prior to direct contact by study staff. Those subjects who respond to advertisements or recruitment letters have implicitly given their permission to be contacted. We will contact potential subjects over the telephone to determine their initial eligibility for and interest in this research study. We will use the attached "Telephone Eligibility Script" and record responses. For those that are interested in participating, we will retain these surveys in accordance with the storage plan outlined in this study for the duration of the study. For those not determined eligible, the surveys will be shredded.

#### **Screening Visit:**

- Obtain and document signed Informed Consent document and HIPAA Authorization.
- Review past medical history in Armed Forces Health Longitudinal Technology Application (AHLTA) to verify the inclusion/exclusion criteria including previous encounter, vital signs review, co-morbidities, demographics, problems list, confirmatory x-rays demonstrating radiographic evidence of knee osteoarthritis.
- We will ask the participants to complete the Screening Visit Medical history questionnaire.
- Record: Age at time of randomization, gender, Kellgren and Lawrence (KL) Grade score at time of enrollment, age at time of osteoarthritis diagnosis, prior knee osteoarthritis therapies to date, name of standard of care medications (over-the-counter and prescription), current email address (to be used for scheduling and weekly email reminders), height (in inches), weight (in pounds), history of prior injury to the affected knee(s), current level of exercise, physical therapy in the past year, and prior experience with mindfulness.

**Randomization:** Subjects will be randomized into 1 of 2 groups using block randomization with repeated measures:

- **Intervention Group:** Patient education regarding osteoarthritis, its natural history, and common treatments plus the mindfulness (intervention) app. They will be provided with a pre-paid 12-week subscription to the mindfulness application, and provided an in-person demonstration on how to use it, and the subscription license code will be recorded for the purposes of tracking use after the conclusion of the study. The intervention group will be asked to use the mindfulness app 10 minutes per day/5 days per week. To standardize Pack usage across all participants, users will be asked to complete the Headspace Essentials", "Pain Management", and "Physical Health" Session Packs.

The intervention application, Headspace, employs short, audio-guided sessions that teach the principles of mindfulness. Participants will register an account within in the application, requiring they provide their name, an email address, and a password. The application will collect usage data, tracking participants' time spent using the application and which specific mindfulness session (known as a "Pack") they used. Aggregate usage data will be provided to the study team by Headspace following the 12-week intervention period, identified only by subscription code. The study team will compare this usage data against participant self-reported use to confirm adherence to the study protocol.

- **Control Group:** Patient education regarding osteoarthritis, its natural history, and common treatments plus the My Water Balance (control) app and provided an in-person demonstration on how to use it. My Water Balance calculates an individual's recommended daily water requirements and assists users in tracking their daily fluid intake. The control group will be asked to log their water intake for the duration of the study, with requested use of 5 days per week to create an equal control. This application is free to download and use. There are options for in-app purchases and application upgrades, though users will be advised against doing so. Information logged in the application may be stored on a third party server; however, no application data will be extracted by the study team. Application use will be reported via weekly surveys, alone.

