**e. Inclusion/Exclusion Criteria:**

Inclusion Criteria	
 
• Male and female Active Duty members and DoD beneficiaries ages 18-74 years
 
• Meet criteria for symptomatic knee osteoarthritis according to the American College of Rheumatology (pain on more than half of the days of the past month during at least one of the following activities: walking, ascending or descending stairs, standing upright, or lying in bed at night)
 
• Demonstrate radiographic evidence of OA, with Kellgren and Lawrence (KL) Grade <math>\geq 1</math> as determined by Lead Site Investigator at each study location
 
• Must have access to a smartphone with enough memory to download the app My Water Balance or the Mindfulness app
 

Exclusion Criteria	
 
• Intra-articular corticosteroid injection in the 3 months prior to participation in the study.
 
• Intra-articular hyaluronic acid/PRP injection in the 6 months prior to participation in the study
 
• Medical condition contraindicating moderate aerobic exercise as determined by their physician
 
• History of knee surgery in the past 6 months or previous knee arthroplasty
 
• Inflammatory joint disease.
 
• Current Practice of Mindfulness
 
• Non-English-speaking
 
• Currently pregnant or planning pregnancy over the study period
 
• Enrollment in other clinical research study during the study period
 
• Inability to comply with treatment protocol, including participation in the Rx3 Home Exercise Program.
 

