### Sample Size Estimation/Power Analysis:

Based on the KOOS Minimal Detectable Changes in patients with knee OA of 10 with a Standard Deviation of 15, a sample size of 74 per group will have 80% power to detect such a difference based on Student's t test for independent samples with 5% two-sided significance level. Allowing for 25% dropout, the required sample size is 99 per group to accomplish the first aim.

However, to determine if high or low strata of baseline mindfulness affects pain outcomes, a sample size of 144 per group (72 in each SF12 stratum) will have 80% power to detect a difference of 10 points with a standard deviation of 15 points (i.e., no mindfulness effect in the high SF12 stratum vs. a 10-point mindfulness effect in the low SF12 stratum). Allowing for the aforementioned 25% dropout rate, we anticipate 180 participants per group or 360 total participants.

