### Number of Subjects:

	# Planned to Enroll	# Enrolled	# Planned to Complete Study	TOTAL
Number of Subjects at Scott AFB	120	0	96	360
Number of Subjects at Travis AFB	120	0	96	
Number of Subjects at Nellis AFB	120	0	96	

*\*If any location recruits more subjects, they will be allowed to continue recruiting not to exceed the total number of subjects for all locations.*

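### The plan does not say that blocks are formed within site, and both ANOVA models leave site out; stratifying and adjusting for site would cost almost nothing

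*Combined protocol and SAP*

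**What the plan says.** **Allocation.** Section 3, Screening Visit, gives one sentence: "Subjects will be randomized into 1 of 2 groups using block randomization with repeated measures". The reference to repeated measures describes how outcomes are collected, not how patients are allocated. The document gives no stratification factor, no block size, no choice between one list and three, no holder of the list and no means of concealment. It also does not say who is blinded.

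**Sites.** Section 3 states: "They will be recruited from the clinics located at Scott AFB, Nellis AFB, and Travis AFB". The Number of Subjects table in section 6 plans 120 at each, but its footnote relaxes this: "If any location recruits more subjects, they will be allowed to continue recruiting not to exceed the total number of subjects for all locations".

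**What is done at site.** Under section 3.e, KL grade is settled "as determined by Lead Site Investigator at each study location". The same table excludes patients for "Inability to comply with treatment protocol, including participation in the Rx3 Home Exercise Program", without saying who judges this or when. The Randomization paragraphs give each arm an in-person demonstration of its own app; the intervention arm is "provided an in-person demonstration on how to use it, and the subscription license code will be recorded".

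**Analysis.** Section 6 (Outcome Measures and Statistical Analysis) names a one-way ANOVA by group for the first aim and a two-way ANOVA, group by baseline stratum, for the second. Neither contains site. Site would be available without extra work, because the coding plan in section 3.f puts a site letter in every study code.

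**The concern.** Site is a plausible source of outcome differences here. Different investigators grade the films, different staff deliver the education and demonstrations, and recruitment may become uneven. The allocation sentence can be read in two ways, and each leaves a gap.

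- **One list across sites.** The overall split is controlled but the split within a site is not, so site differences can enter the arm comparison by chance.
- **One list per site.** Site balance is controlled, but the ANOVA then ignores the strata used to randomise. Staff who know past allocations may also infer some future ones, depending on block size and concealment, neither of which is stated.

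Under both readings, between-site variance in change in KOOS pain stays in the residual. What is at stake is some precision, mainly for the interaction aim, and a clear defence of the allocation procedure.

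**Working it through.** **Inputs from the document.** 360 patients, 180 per arm, three sites of 120 (section 6); difference 10, SD 15, two-sided 5%, 72 per cell for the interaction (Sample Size Estimation).

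**Assumptions.** Block size, the spread of site means and the between-site SD are not in the document. Ranges are shown for each.

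**1. Within-site imbalance if one blocked list serves all sites**

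Code the arms +1 and −1, and let patients arrive from the sites in random order. The variance of the arm difference in a site of 120 is 120 − 120 × 119/359 = 80.2, whatever the block size. The SD of the difference is therefore 8.96, and the SD of the arm count is 8.96/2 = 4.5. Independent assignment would give √120/2 = 5.5, which overstates it.

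Simulation with blocks of 2, 4, 6 and 8 agrees (SD of the difference 8.9 to 9.0). The median worst-site split is 65:55. The chance that some site is 70:50 or worse is 8 to 9% (8.6% for blocks of 4).

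**2. What that imbalance does to the arm comparison**

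Suppose site means of −5, 0 and +5, a 10-point spread. The shift in the arm difference is (5/180) × (d₃ − d₁), where d₁ and d₃ are the arm differences at the two outer sites. The three differences sum to zero, so Var(d₃ − d₁) = 3 × 80.2 = 240.7, with SD 15.5. The shift therefore has SD 5 × 15.5/180 = 0.43 points; 95% of simulated shifts lie within 0.83. A 5-point spread halves this to about 0.21.

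The standard error of the arm difference is 15 × √(2/180) = 1.58 with everyone analysed, and 15 × √(2/144) = 1.77 with 144 per arm.

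**3. Power of the interaction test**

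Power = Φ(10/(SD × √(4/72)) − 1.96).

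Plan's figure: SD 15 gives a standard error of 3.536, so Φ(2.828 − 1.96) = 80.7%. The stated 80% is reproduced.

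With a site term, if 15 is the total SD and t the between-site SD, the residual SD is √(225 − t²):

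| t (assumed) | Residual SD | Power with site term |
|---|---|---|
| 3 | 14.70 | 82.3% |
| 5 | 14.14 | 85.1% |
| 7 | 13.27 | 89.2% |

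If allocation is already blocked within site, the model without site overstates its standard error, and its power lies somewhat above 80.7%. At full site balance with t = 5 it would be Φ((10 − 1.96 × 3.536)/3.333) = Φ(0.92) = 82%. The gain is then nearer 3 points than 4.

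**4. The first aim**

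At 74 per group with the plan's 10 and 15, power = Φ(10/(15 × √(2/74)) − 1.96) = 98.2%, so a site term has little to add. (The plan states 80% there; that is a separate matter.)

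**5. Predictability, by type of list**

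| List (block size assumed) | Correct guesses | Certain allocations |
|---|---|---|
| Site-specific, fixed blocks of 4, all visible to staff | 70.8% | 33% |
| Site-specific, fixed blocks of 6, all visible to staff | 68.3% | 25% |
| One shared list, site sees only its own third, blocks of 2 to 8 (guessing the opposite of its last allocation) | 55 to 58% | not computed |

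**The case against.** The strongest reply is that this is silence, not a poor choice. If each site keeps its own block list, the trial is stratified in effect. With about 120 per site, chance imbalance is minor and already covered by the test's error rate. Most of this stands, and it rules out four stronger readings that a reader might reach.

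- **That the plan rejects stratification by site.** It does not say so; it leaves the point open.
- **That short blocks make the next allocation guessable.** No block size is given. The 70.8% and 68.3% rates need site-specific fixed blocks whose whole sequence staff can see. They do not apply to a shared list, the only reading under which site imbalance arises, so the two harms should not be added together.
- **That staff can steer likely non-compliers.** Section 3.e does not say who judges ability to comply, and the Screening Visit lists the eligibility check ahead of randomisation. What is missing is a statement that eligibility is recorded as final before the allocation is released.
- **That leaving site out cuts Aim 2 power to 76.5%.** That figure adds a site SD of 5 on top of 15. The Sample Size section never says that 15 is a within-site SD. If it is the total, power remains 80.7% as planned, and site adjustment is a gain forgone.

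The trial also cannot be called unblinded on the document's word. Knowledge of the arm is a fair inference for anyone who demonstrates or uses one of two different apps, but no blinding statement is made.

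The reply does not answer the analysis point. The ANOVA models are specified, and they leave out a factor that is known for every patient and that should be in the model if allocation is blocked within it.

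**Conclusion.** The point holds as a modest, cheaply corrected weakness: stratification by site is not stated, and site is absent from both stated models.

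Under one shared list, the harm is chance imbalance: an arm-count SD of about 4.5 in 120, and a shift in the arm difference of SD 0.43 points even for a 10-point spread of site means, against a standard error of 1.58 to 1.77 and a target of 10. This is random error, not bias. Under site-specific lists, the analysis does not match the randomisation.

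A site term would lift Aim 2 power from about 81% to about 85%, or to between 82% and 89% for site SDs of 3 to 7. This rests on 15 being the total SD and on an assumed site SD. The first aim gains little. Selection bias through prediction remains possible only because block size and concealment are not described; the document does not show that it would occur.

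**What to change.** Replace the allocation sentence in section 3 with wording such as:

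> *Participants will be randomised 1:1 within site, using permuted blocks of randomly varied size. Block sizes are withheld from enrolling staff. The list is generated and held by a team member who does not enrol. Each allocation is released only after eligibility, including ability to follow the home exercise programme, has been recorded as final.*

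Add a sentence on who knows the allocation. In section 6, add site as a factor to the one-way and the two-way ANOVA.

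The parts belong together. Blocking within site limits the arm difference at a site to half a block (2 patients for blocks of 4), but on its own it makes the sequence easier to predict. Varied, withheld block sizes and concealed release counter that.

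The cost is a three-stratum list, one extra model term with 2 degrees of freedom, and a paragraph of text, with no extra patients. The Number of Subjects table shows none enrolled, so the allocation can still be specified in advance. If enrolment has begun, the site term can still be added before the data are analysed.
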